3 SYNOPSIS

Device:	/leva Incontinence System™
Clinical Indication:	Urinary Incontinence
Study Objective:	The objective of this study is to assess the effectiveness of the /leva Incontinence System™ in treating bladder incontinence.
Summary of Study Design:	
An open-label study.
 
Screening of subjects will occur over 1-2 study visits to determine study eligibility.
 
Up to 25 subjects meeting inclusion/exclusion criteria at Screening will complete about 6-8 weeks of training and testing with a device to improve the strength of their pelvic floor muscles.
 
Weekly during the study the subjects will complete tests using the /leva device to assess changes in their pelvic floor muscle strength. Subjects will also complete surveys to assess improvements in the symptoms of their urinary incontinence.
 
The FSFI and PISQ-IR surveys will be provided to subjects to complete at the Screening visit and upon study completion and will be returned in a sealed envelope for review after conduct is completed. Completion of the FSFI and PISQ-IR surveys is optional.
 
Subjects that complete the study will be asked to participate in an optional post study interview with the Study Director and a marketing professional to better understand the subjects' experience using the device. The interview is optional.

Blinding:	Unblinded
Number of Subjects:	Up to 25 subjects meeting inclusion/exclusion criteria at Screening visit will return to the clinic to participate in the treatment phase of the study.
Study Treatment:	/leva Incontinence System™
Key Assessments:	
The following analyses will be performed:
 
Efficacy:
 
• /leva device angle measurements• Survey evaluations of incontinence including:
○ Urinary Incontinence Distress Inventory (UDI-6)○ Incontinence Impact Questionnaire (IIQ-7)

	
○ Patient's Global Impression of Severity (PGI-S)○ Revised Urinary Incontinence Scale (RUIS)○ Patient's Global Impression of Improvement (PGI-I)○ Clinician's Global Impression of Improvement (CGI-I)○ Voiding diary 
Safety and Tolerability:
 
○ Subjects will be monitored for adverse events and serious adverse events.
--	--

4 STUDY EVENTS FLOW CHART

Study Procedures	Screen	Training Visits	Week 3	Week 6 Visit	End of Study/Early Termination
Visit →	1**	2-30	11	26	31
Inclusion/Exclusion Criteria	X				
Informed Consent	X				
Demographic data	X				
Medical History	X				
Height/Weight	X				
Urine Pregnancy Test	X				
Oral alcohol/Urine Drug Screen	X				
AE Monitoring		X	X	X	X
Concomitant Medication	X	X	X	X	X
Survey: MESA	X				
Surveys: UDI-6, IIQ-7, PGI-S, RUIS	X	X weekly	X	X	X
Surveys: FSFI, PISQ-IR (optional)	X				X
Patient's & Clinical Global Impression-Improvement			X	X	X
Voiding Diary	X		X		X
leva Training	X	X	X	X	
leva Testing/Angle Measurements	X	X* visits 6, 16 & 21	X*	X*	X*
Interview subject about experience using the device (optional)					X

*Preferably on Mondays

** Screening activities can be conducted over 1-2 visits

5 ABBREVIATIONS

AE	Adverse event
CFR	Code of Federal Regulations
CGI-I	Clinical Global Impression of Improvement
CRF	Case Report Form
CRU	Clinical Research Unit
EOS	End of Study
FDA	Food and Drug Administration
FSFI	Female Sexual Function Index
GCP	Good Clinical Practice
ICF	Informed Consent Form
ICH	International Conference on Harmonisation
IIQ-7	Incontinence Impact Questionnaire
IRB	Institutional Review Board
MESA	Medical, Epidemiologic and Social Aspects of Aging
N	Number of subjects
PGI-I	Patient's Global Impression of Improvement
PGI-S	Patient's Global Impression of Severity
PI	Principal Investigator
PISQ-IR	Pelvic Organ Prolapse/Incontinence Sexual Questionnaire
QA	Quality Assurance
RUIS	Revised Urinary Incontinence Scale
SAE	Serious adverse event
SAP	Statistical analysis plan
SD	Standard deviation
UAE	Unexpected adverse event
UDI-6	Urinary Incontinence Distress Inventory
US	United States

6 BACKGROUND

Injury or weakening of the pelvic floor muscles can lead to pelvic floor disorders including urinary incontinence, pelvic organ prolapse, fecal incontinence or sexual dysfunction. These conditions affect 1 in 4 women of all ages and can make a significant impact on quality of life. Pelvic Floor Muscle Exercises, also known as Kegel's, are the first-line conservative treatment for pelvic floor disorders and specifically for urinary incontinence. Studies have shown that performing pelvic floor muscle exercises and/or pelvic floor physical therapy is the most effective non-invasive treatment for urinary incontinence. Pelvic Floor Muscle Therapy is advocated as the first-line of treatment for urinary incontinence by the American College of Obstetrics and Gynecology, the American Urogynecological Society, the Agency for Healthcare Research and Quality.

Pelvic Floor Muscle Exercises was first described by Arnold Kegel almost 60 years ago. Most women have trouble identifying and contracting the correct muscles when performing these exercises. The novel device that is an intravaginal system, *leva* Incontinence System™ allows women to have real-time visual verification that the exercises are performed correctly and consistently. *leva* Incontinence System™ also measures and records the results of every session performed while using the device thus assuring patient compliance. In the proposed study we aim to clinically show improvement of incontinence symptoms with use of *leva* Incontinence System™ for performing Pelvic Floor Muscle Exercises.

The association between urinary incontinence and female sexual dysfunction has been described in the literature. The relationship is reported by Salonia et al (2004) however, overall there is a paucity of research in this area. We will evaluate if women who show improvement in incontinence symptoms with the use of the *leva* Incontinence System™ and who complete the optional FFSI and PISQ-IR surveys have changes in their responses to the survey questions and will then determine if further research is warranted.

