7 STUDY OBJECTIVE AND ENDPOINT

7.1 Study Objective

The objective of this study is to assess the effect of the *leva* device on signs and symptoms of urinary incontinence as measured by the endpoints described below.

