8 INVESTIGATIONAL PLAN

8.1 Overall Study Design and Plan

An open-label study in adult women with urinary incontinence.

Screening of subjects will occur in one to two visits to determine study eligibility.

Up to 25 subjects meeting inclusion/exclusion criteria at screening will participate in 6 (up to 8 weeks) of twice daily training sessions using the *leva* device. Subjects will be allowed up to 8 weeks to complete the study to accommodate scheduling issues, menstrual periods or planned vacations.

Training sessions last 2.5 minutes with alternating 15 seconds of voluntary contraction of the pelvic floor muscles and 15 seconds of rest.

Changes in urinary incontinence will be assessed by symptoms of incontinence, *leva* angle measurements and patient's and clinician's assessment of global improvement over the study period.

All subjects enrolled in the study will be asked to complete the FSFI and PISQ-IR surveys upon enrollment and at study end. Completion of the FSFI and PISQ-IR is optional, and completed surveys will be returned in a sealed envelope and reviewed following study completion.

All subjects who complete this study will be invited to participate in an optional interview with the Study Director and a marketing professional to better understand their experiences using the device. The interview will last up to one hour at the final visit.

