Frequency: once a day 5 days a week. The female leva Trainer will supervise the participants on performing 2 1/2 minutes of 5 repetitions of pelvic floor exercises using the leva Incontinence System TM (leva Training)

Once a week, preferably Mondays, during the about 6-8 week study period:

The subjects will be asked to perform a series of 5 exercises “leva Test” to test the effect of the daily training and follow the test with the 2 ½ minutes of training (leva Training). The female leva Trainer will record leva device measurements.

The study participants will be given the following surveys:

- UDI-6
- IIQ-7
- PGI-S
- RUIS

At 3 weeks:

The subjects will be asked to perform a series of 5 exercises (leva Test) to test the effect of the daily training and follow the test with the 2 ½ minutes of training (leva Training). The female leva Trainer will record leva device measurements.

The study participants will be given the following questionnaires:

- UDI-6
- IIQ-7
- PGI-S
- PGI-I
- RUIS
- Voiding diary completion

The Study Director or PI will complete the Clinician’s Global Impression of Improvement (CGI-I) evaluation.

At 6 weeks:

The subjects will be asked to perform a series of 5 exercises (leva Test) to test the effect of the daily training and follow the test with the 2 ½ minutes of training (leva Training). The female leva Trainer will record leva device measurements.

The study participants will be given the following questionnaires:

- UDI-6
- IIQ-7
- PGI-S
- PGI-I
- RUIS

The Study Director or PI will complete the Clinician’s Global Impression of Improvement

(CGI-I) evaluation.

At the End of Study/ Early Termination visit:

The subjects will be asked to perform a series of 5 exercises (*leva* Test) to test the effect of the daily training. The female *leva* Trainer will record *leva* device measurements.

The study participants will be given the following questionnaires:

- UDI-6
- IIQ-7
- PGI-S
- PGI-I
- RUIS
- Voiding diary completion
- FSFI (optional)
- PISQ-IR (optional)

The Study Director or PI will complete the Clinician's Global Impression of Improvement (CGI-I) evaluation.

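### Section 6 evaluates FSFI and PISQ-IR change only in women whose incontinence improved, so the result cannot separate change that tracks incontinence from a general shift in answers

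*Combined protocol and SAP*

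**What the plan says.** The paragraph in Section 6 (Background) opens with the motivation: "The association between urinary incontinence and female sexual dysfunction has been described in the literature". After noting how little research exists, it states one evaluation: "We will evaluate if women who show improvement in incontinence symptoms with the use of the" device, and who complete the optional surveys, "have changes in their responses to the survey questions and will then determine if further research is warranted".

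The other mentions concern administration:

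- Section 8.1: "All subjects enrolled in the study will be asked to complete the FSFI and PISQ-IR surveys upon enrollment and at study end". Completion is optional, and "completed surveys will be returned in a sealed envelope and reviewed following study completion".
- Section 3 (Synopsis) agrees that the surveys "will be returned in a sealed envelope for review after conduct is completed".
- The Section 4 flow chart and Section 9 place both surveys at screening and at the end-of-study or early-termination visit. They place UDI-6, IIQ-7, PGI-S and RUIS at those same two points, among others.

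The objective in Section 7.1 concerns "signs and symptoms of urinary incontinence as measured by the endpoints described below", and the Section 7.2 list contains neither FSFI nor PISQ-IR. Section 10.1 leaves detailed methods to the Clinical Study Report. No section defines improvement for this purpose or names a comparison with women who did not improve.

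**The concern.** The paragraph starts from a relation between two conditions and ends with a decision about pursuing that relation. The evaluation in between looks at one side only: women already selected because their incontinence got better. In an unblinded study with no control arm, survey answers can shift between two time points for reasons unrelated to incontinence. If they shift for everyone, improvers will show the shift too. If they move only with incontinence, improvers will again show a change. The stated subset gives the same kind of result in both cases.

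At stake is the one use the protocol names for these data, the judgement on further research. The data that could tell the two cases apart are already scheduled, because every enrolled woman is asked for both surveys at both time points.

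**Working it through.** The plan gives no figure to reproduce for these surveys. Section 10.1.1 says that the sample size had no statistical basis. The check is therefore one of logic, with an illustration on assumed inputs.

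**Inputs from the documents.** Up to 25 women, one arm, each her own control (Sections 8.1 and 10.1.1); both surveys at screening and study end, optional; UDI-6 at the same points.

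**Assumptions, not in the documents.** Incontinence change and survey change are standardised and jointly normal with correlation ρ. A share p of women are improvers. The number returning both surveys is 25 (the maximum) or 15.

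**Step 1: what the improver mean contains.** With c = z(1-p) and φ the normal density:

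- improver mean = all-women mean + ρ·φ(c)/p
- non-improver mean = all-women mean - ρ·φ(c)/(1-p)

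The improver mean is one number with two unknowns behind it, the general shift and ρ.

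**Step 2: the same improver mean under different truths.** Take p = 0.7. Then c = -0.524, φ(c) = 0.348, φ(c)/p = 0.497 and φ(c)/(1-p) = 1.159. Fix the improver mean at +0.20 SD.

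| ρ | All women | Non-improvers |
|---|---|---|
| 0 | +0.20 | +0.20 |
| 0.2 | 0.20 - 0.2×0.497 = +0.10 | 0.101 - 0.2×1.159 = -0.13 |
| 0.5 | 0.20 - 0.5×0.497 = -0.05 | -0.048 - 0.5×1.159 = -0.63 |

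All three rows give the reader of an improvers-only summary the same +0.20 SD.

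**Step 3: a second case, by simulation.** Take p = 0.6 with 25 completers and 4,000 runs per case. With ρ = 0.5 and no general shift, the improver mean is 0.317 SD. With ρ = 0 and a general shift of 0.322 SD, it is 0.323 SD. The two cases again cannot be told apart from improvers alone.

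**Step 4: how precise the wider analysis would be.**

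- Mean paired change in all completers: 95% half-width = t(0.975, n-1)/√n, which is 2.064/5 = 0.41 SD at n=25 and 2.145/3.873 = 0.55 SD at n=15.
- Correlation by Fisher z, observed r = 0.3: 0.3095 ± 1.96/√22 back-transforms to -0.11 to 0.62 at n=25; 0.3095 ± 1.96/√12 gives -0.25 to 0.70 at n=15.
- Improvers minus non-improvers: half-width 0.84 SD at 15 against 10, and 1.03 SD at 20 against 5.

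The relation can be estimated from the scheduled data, but only with a wide interval.

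**The case against.** The strongest reply is that Section 6 asks only whether improvers' answers change, and that a before/after summary in improvers answers exactly that. Looking for change where it is most expected is a reasonable screen. The sentence also sits in the Background and concerns instruments outside the objective and endpoints, while methods for all data are deferred to the study report. Much of this stands: the summary is correct for the women it describes, and the matter is exploratory. It does not remove the point. The sentence is the only statement of how these surveys will be used, it names a subset, and following it gives a result that cannot speak to the association that motivates it.

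A second reply is that the added analysis will seldom settle anything. This is partly right. In the ρ = 0.5 row above, the group difference is 0.20 + 0.63 = 0.83 SD, while 18 improvers against 7 non-improvers gives a 95% half-width of about 0.92 within-group SD. A correlation uses all the data and avoids the cut-off, but is also imprecise. That argues for description, not for leaving non-improvers out.

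Four stronger readings are tempting and are not supported:

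- *The plan states no contrast at all.* Changed responses across two time points imply a within-woman comparison. What is missing is a comparison between women.
- *The improver figure will overstate the effect in all treated women.* No section extends the result beyond improvers, so any such overstatement is hypothetical. Its size and sign would depend on an unknown correlation.
- *Non-improvers are excluded.* All women are offered the surveys, and review of completed surveys is not limited to improvers. The plan is silent on their analysis; it does not bar it.
- *A planned test is invalid.* No test or significance level is stated for these surveys.

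A correlation of changes within improvers would carry some range-restricted information, but none is stated either.

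**Conclusion.** The point holds in this limited form. The only stated FSFI and PISQ-IR evaluation is confined to a group selected on outcome, with no comparison with non-improvers or with degree of improvement. A summary of that group cannot separate change that follows incontinence from a general shift.

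The logic rests on the text alone. The +0.20 SD example is illustrative and depends on the assumed 70% improvers, the assumed correlations and joint normality; the documents supply none of these. The share of improvers and the survey return rate are unknown.

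A related gap is that improvement is undefined. Section 7.2 lists seven survey or diary measures besides the device angles, so the stated subset cannot be reproduced as written.

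This is an optional, low-priority improvement. No efficacy or safety conclusion is affected; only the judgement on further research is.

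**What to change.** Replace the last sentence of Section 6 with text to this effect:

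1. Report paired FSFI and PISQ-IR change with a 95% CI in every woman who returns both administrations, whether or not her incontinence improved, and state how many of those enrolled did so.
2. Describe the relation of that change to change in one named incontinence score already collected at screening and study end (for example UDI-6), as a scatter plot and a correlation with its CI, labelled exploratory and with no significance claim.
3. If improvers are shown separately, fix the measure and cut-off in writing before the sealed surveys are opened, and show non-improvers beside them.

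The cost is one reworded sentence and a little more analysis. No visit, survey or subject is added. The all-completer figure may be less favourable than the improver figure, and its interval will be wide. Non-improvers may be few (5 of 25 if 80% improve). Some limits remain: return of the surveys is voluntary, two self-reports in an unblinded study may share reporting effects, and an association in a single arm does not show cause.

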7 STUDY OBJECTIVE AND ENDPOINT

7.1 Study Objective

The objective of this study is to assess the effect of the *leva* device on signs and symptoms of urinary incontinence as measured by the endpoints described below.

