8.4 Treatments

8.4.1 Treatment Administered

Subjects will train twice daily for 6 (up to 8 weeks) using the *leva* device. The female *leva* Trainer will assist the subject five days a week with the training session by helping to assure that the subject is performing the training using the correct muscle movements.

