10.1.1 Determination of Sample Size

This is an open-label study where subjects serve as their own control. The sample size was selected without statistical considerations.

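### The stated objective is the effect of the leva device, but a single-group before/after study of device, exercise and coaching together can only describe change under the whole program

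*Combined protocol and SAP*

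**What the plan says.** The protocol words its purpose in three ways.

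- Section 7.1 (Study Objective): "The objective of this study is to assess the effect of the" leva device on signs and symptoms.
- Section 3 (Synopsis): "The objective of this study is to assess the effectiveness of the" leva system in treating incontinence.
- Section 6 (Background), more narrowly: "In the proposed study we aim to clinically show improvement of incontinence symptoms with use of" leva as a means of doing pelvic floor exercises.

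The design is given in Section 8.1 as "An open-label study in adult women with urinary incontinence", and in Section 10.1.1: "This is an open-label study where subjects serve as their own control". There is one group of up to 25.

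On treatment, Section 8.4.1 has every subject train twice daily with the device, and a trainer attends five days a week "by helping to assure that the subject is performing the training using the correct muscle movements". Section 9 shows that this coaching takes place during the device sessions.

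The Background says that "performing pelvic floor muscle exercises and/or pelvic floor physical therapy is the most effective non-invasive treatment for urinary incontinence", and that the device "allows women to have real-time visual verification that the exercises are performed correctly and consistently". It adds that the device records each session.

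Section 10.1 leaves the analysis methods to the Clinical Study Report.

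**The concern.** The objective names the device as the cause whose effect is to be assessed. The design has no feature that isolates it: no concurrent arm doing the same coached exercise without the device, no untreated arm, no run-in period, no external benchmark and no performance goal. The protocol's own account makes the other ingredients active, because it ranks exercise and/or physical therapy first among non-invasive treatments and has a trainer help with correct technique.

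What is at stake is the conclusion. Since the methods are deferred to the report, the objective is the main text that governs what the report may claim. A report that follows it literally would credit the device with change that may come wholly or partly from other sources.

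**Working it through.** **No figure to reproduce.** The protocol gives no effect size, power or alpha, and says that the sample size had no statistical basis. The check is mainly one of reasoning.

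**1. What a before/after change contains.** For each subject, the change from baseline is

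observed change = device + exercise + coaching + time + expectation + regression to the mean.

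All of these begin together in every subject. The data give one mean change per endpoint, and nothing varies between subjects by design. One equation with several unknowns cannot be solved for the device term, and more subjects in the same single group would only estimate the sum more precisely.

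**2. Which non-device terms are plausible here.**
- Exercise and coaching: Sections 6 and 8.4.1, as quoted above.
- Regression to the mean: Section 8.3.1 admits subjects on the results of incontinence surveys. It does not say which, but UDI-6, IIQ-7, PGI-S and RUIS are given at screening and are also endpoints in Section 7.2.
- Expectation: most endpoints are self-reported, and the unblinded Study Director or PI rates CGI-I (Section 9).
- PGI-I and CGI-I are not collected at screening (Section 4), so they have no baseline value at all.

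**3. How much training is supervised.** Training with the trainer occurs at the screening visit and at visits 2 to 30: 1 + 29 = 30 sessions. Planned sessions at two a day depend on assumptions that the protocol does not settle:

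| Assumed training | Planned sessions | Supervised share |
|---|---|---|
| 5 days a week, 6 weeks | 2 × 5 × 6 = 60 | 30/60 = 50% |
| 7 days a week, 6 weeks | 2 × 7 × 6 = 84 | 30/84 = 36% |
| 7 days a week, 8 weeks | 2 × 7 × 8 = 112 | 30/112 = 27% |

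The unsupervised sessions also use the device, so comparing the two kinds of session would not isolate it.

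**4. Illustration, on assumed inputs.** Suppose that the device's own effect is zero, n = 25, and a two-sided 0.05 paired t-test is used (the protocol specifies no test). Let non-device change be d standard deviations of the change score. The probability of significant improvement is

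P = 1 − F(t; 24 df, noncentrality d√25 = 5d), where t is the 97.5th percentile of the central t distribution with 24 df.

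| d (assumed) | Noncentrality | P |
|---|---|---|
| 0 | 0 | 2.5% |
| 0.3 | 1.5 | 30% |
| 0.5 | 2.5 | 67% |
| 0.8 | 4.0 | 97% |

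A significant result could therefore be likely with no device effect. None of these d values comes from the documents.

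**The case against.** The best case for the plan is that it never poses the incremental question. Nowhere does it claim superiority over exercise alone or over coaching. The Background aim and Section 8.1 speak of improvement and of changes over the study period, which a before/after study can describe. The open-label, unblinded design is disclosed. Entry criteria exclude concurrent supervised exercise, supervised rehabilitation in the past 12 months and current incontinence medication, so some competing causes are limited.

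Much of this stands, and it rules out several stronger readings that a reader might infer:

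- *That there is no comparator at all.* Baseline is one, and it supports a statement about change over time. Only a concurrent comparator is missing.
- *That coaching is a separate program alongside the device, or that the trainer duplicates the device.* The coaching is given within device sessions. The device also gives visual feedback and records home sessions, which the trainer does not attend.
- *That the Background credits improvement to exercise alone.* Its sentence includes physical therapy, and it goes on to say that most women struggle to contract the right muscles, which is the device's rationale.
- *That describing subjects as their own control is an error.* It is ordinary before/after language, and changing it is mostly preference.
- *That a single-group study is illegitimate.* It is a reasonable pilot design for a descriptive aim.

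What does not stand is the defence that the objective is mere shorthand. Section 7.1 and the Synopsis go beyond the Background aim, that aim itself leaves out the trainer, and no sentence confines the conclusion to the package. It is also true that no sentence promises a device-specific conclusion. The risk lies in a report following the objective as worded.

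**Conclusion.** The concern holds as a mismatch between the objective and what the design can show. The data can describe change from baseline under trainer-supervised exercise with leva. They cannot show the device's own contribution.

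Its size cannot be put as a share of the observed change. Any split between device and non-device causes would be an assumption that these data could not contradict. The supervised share of sessions, 27% to 50%, describes how much coaching the package contains. It does not measure bias. The probabilities in the illustration depend on the assumed d and on the assumed test.

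The data remain usable and no procedure is faulty. What should change is the claim.

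**What to change.** - **Section 7.1 and Synopsis:** bring the objective into line with the narrower Background aim and name the trainer. For example: *describe change from baseline in urinary incontinence measures over a 6–8 week program of trainer-supervised pelvic floor exercise performed with leva.*
- **Section 10:** state that results are uncontrolled before/after changes, and that no conclusion on the device's own contribution will be drawn from them.

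This is wording only: no new arm, data or procedure. The cost is a less favourable claim.

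If the sponsor wants the device-specific question answered, that is a different study, with a concurrent arm of the same coached exercise without the device. With 1:1 allocation, two-sided alpha 0.05 and 80% power, n per arm = 2(1.96 + 0.84)²/d². For assumed standardized differences of 0.3, 0.5 and 0.8, this gives about 175, 63 and 25 per arm before dropout. Splitting 25 subjects 1:1 would give power Φ(d√(12.5/2) − 1.96), about 11%, 24% and 52%. Adding an arm within the present sample size would therefore not rescue the current objective, and rewording is the proportionate change.
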